#### *Pharmacokinetics in healthy subjects*

Following both single and multiple doses of 10 and 15 mg, BI 1467335 Cmax and AUC0-24 increased in a more than dose proportional manner on Days 1, 14 and 28 ([Figure 1.2: 1](#)). Resulting from the accumulation of BI 1467335 following repeat oral dosing, quantifiable BI

Proprietary confidential information © 2018 Boehringer Ingelheim International GmbH or one or more of its affiliated companies

1467335 concentrations could be measured up to 4 h and 8 h postdose for 10 and 15 mg respectively on Day 1; and up to 24 h postdose on Days 14, and Day 28. Resulting from the limited time period over which quantifiable BI 1467335 concentrations could be measured on Day 1; the resulting  $AUC_{0-24}$  values on Day 1 need to be regarded with caution, as they may be underestimates, due to the large number of concentrations below the assays lower limit of quantification

The observed apparent elimination half-life (gMean) for BI 1467335 is significantly shorter on Day 1 (<1 h) compared to Days 14 and 28, (<4 h following 10 mg and < 9 h following 15 mg on Day 28). Despite the short apparent elimination half-lives, BI 1467335 significantly accumulates following q.d. dosing. For 10 mg q.d.,  $C_{max}$  increased by approximately 26-fold on Day 14 and 40-fold on Day 28, and  $AUC_{0-24}$  increased by approximately 58-fold on Day 14 and 159-fold on Day 28. For 15 mg q.d. dosing,  $C_{max}$  increased by approximately 14-fold on Day 14 and 16-fold on Day 28, and  $AUC_{0-24}$  increased by approximately 72-fold on Day 14 and 82-fold on Day 28.

Taking all the BI 1467335 data together, including trough concentrations, 1 h postdose samples along with  $AUC_{0-24}$  values, they suggest that steady state may be attained close to Day 14 following 15 mg q.d., whereas it was not attained by Day 14 following 10 mg q.d.. Following 10 mg q.d.,  $C_{max}$  and  $AUC_{0-24}$  are approximately 54% and 180% higher respectively on Day 28 compared to that on Day 14, whereas following 15 mg q.d.,  $C_{max}$  and  $AUC_{0-24}$  are approximately 13 and 15 % higher respectively on Day 28 compared to that on Day 14. For further details, please refer to the current 'Investigator's Brochure (IB)' [\[c04751792\]](#).

Thus, BI 1467335 appears to display both dose and time dependent kinetics, where BI 1467335  $C_{max}$  and  $AUC_{0-24}$  values on Days 14 and 28 are greater than predicted from Day 1 data. BI 1467335 accumulation may in part be due to irreversible binding to AOC3 enzymes which are present in many different tissues within the body (Target Mediated Drug Disposition). This may explain the observation that steady state appears to be attained earlier following 15 versus 10 mg q.d. the highest dose tested to date.

[figure not shown]

Figure 1.2: 1

Geometric Mean BI 1467335 concentration-time profiles following single and multiple BI 1467335 dosing, 10 mg q.d. (left graph) and 15 mg q.d. (right graph), to healthy subjects on Days 1, 14 and 28 (up to 24 h postdose, semi-log scale)

#### *Pharmacodynamics in healthy subjects*

AOC3 activities and their change from baseline were determined throughout study PXS-4728A-101 [[c09036683](#)]. During the SRD part of the study, a strong, dose related response to AOC3 activity inhibition could be demonstrated with increasing numbers of subjects achieving a reduction of 90% with increasing doses. At the highest single dose of 20 mg, AOC3 inhibition of greater than 90% was reported up to 12 hours post-dose in 5 of 6 subjects, with the mean SSAO inhibition at 24 hours being greater than 80%. The maximum inhibition was observed within 2 hours of single dose administration for most subjects across all dose groups.

During the MRD part of the study, inhibition of AOC3 activity at 24 hours post-dose on Day 14 remained greater than 90% for all subjects receiving a daily dose of 6 or 10 mg BI 1467335. At the lowest repeat dose level of 3 mg BI 1467335 per day, the AOC3 inhibition was greater than 80% at 24 hours post-dose on Day 14 in all subjects.

For further details, please refer to the current 'Investigator's Brochure (IB)' [[c04751792](#)].

## **2. RATIONALE, OBJECTIVES, AND BENEFIT - RISK ASSESSMENT**

### **2.1 RATIONALE FOR PERFORMING THE TRIAL**

An association between NAFLD/NASH and impaired renal function was consistently shown in numerous epidemiological studies [[P16-05590](#)] and may be due to common underlying inflammatory pathways in liver and kidney. BI 1467335 is going to enter phase IIb in a NASH population. Taking the published epidemiological data into consideration this may be associated in up to 20% of NASH patients with a reduced GFR < 60 ml/min i.e. at least moderate renal impairment.

Based on both the preclinical and ongoing clinical phase I study 1386.8, renal clearance is considered to be involved in the elimination of BI 1467335, especially following multiple dosing. The study is conducted to support the safe inclusion of NASH patients who may have moderate renal impairment in Phase IIb/III studies.

The PK will be investigated during a 4 week treatment with 10 mg of BI 1467335 q.d. which has already been shown to be well tolerated in healthy subjects. A dose of 10 mg is the planned maximum therapeutic dose in a NASH population. Currently 20 mg q.d. is being investigated in HVs. Preliminary 15 mg q.d. in HVs on Day 28 resulted in gMean  $C_{max}$  and  $AUC_{0-24}$  values approximately 2.6 and 4.7-fold higher than those observed on Day 28 following 10 mg q.d..

### **2.2 TRIAL OBJECTIVES**

The primary objective of the current study is to investigate the influence of moderate renal impairment on the pharmacokinetics of multiple doses in comparison to a matched control group with normal renal function.

The assessment of safety and tolerability will be an additional objective of this trial.

A description of the endpoints to be determined, and the observations along with specific information as how to collect the data for that information, is provided in [Section 5](#).

### **2.3 BENEFIT - RISK ASSESSMENT**

Participation in this study is without any (therapeutic) benefit for healthy subjects or subjects with moderate renal impairment. Their participation in the study, however, is of major importance to the clinical development of BI 1467335. The subjects are exposed to the risks of the study procedures and the risks related to the exposure to the trial medication.

#### Procedure-related risks

The use of an indwelling venous catheter for the purpose of blood sampling may be accompanied by mild bruising and also, in rare cases, by transient inflammation of the wall of the vein. In addition, in rare cases a nerve might be injured while inserting the venous catheter, potentially resulting in paresthesia, reduced sensibility, and/or pain for an indefinite period. The same risks apply to veinipuncture for blood sampling.

Proprietary confidential information © 2018 Boehringer Ingelheim International GmbH or one or more of its affiliated companies

The total volume of blood withdrawn during the entire study period of 6 weeks will not exceed about 300 mL per subject. This is less than the volume of a normal blood donation (500 mL). No health-related risk to the subjects is expected from this blood withdrawal.

#### Drug-related risks and safety measures

Assessment of drug related risks is mainly based on data of an ongoing phase I study investigating safety, tolerability and pharmacokinetics of 10 mg, 15 mg and 20 mg q.d. of BI 1467335 for 28 days in healthy subjects. Data have been obtained for the complete 10 mg dose group (9 on active and 3 on placebo) and 7 subjects (5 on active and 2 on placebo) who completed the 15 mg q.d. treatment. The 20 mg q.d. dose group has recently completed treatment as well, however data evaluation is still ongoing. Regarding the 10 mg and 15 mg dose group and as already observed in a preceding 2 week study [[c09036683](#)] there were no SAEs and no AEs considered to be dose limiting. Nearly all of the AEs were of mild intensity. One subject assigned to 15 mg q.d. discontinued after receiving the 5th dose because of a common cold. There were no changes in safety labs, vital signs or ECGs readings considered to be clinically relevant. While the evaluation of the 20 mg dose group is ongoing there were no SAEs and no AEs considered being dose limiting as well. These findings are consistent with results of a preceding SRD/MRD study investigating a dose range of up to 10 mg of BI 1467335 administered for 14 days.

Following both single and multiple doses of 10 and 15 mg of BI 1467335  $C_{max}$  and  $AUC_{0-24}$  increased in a more than dose proportional manner on Days 1, 14 and 28 [[c04751792](#)]. Despite the short apparent elimination half-lives, BI 1467335 significantly accumulates following q.d. dosing. For 10 mg q.d.,  $C_{max}$  increased by approximately 26-fold on Day 14 and 40-fold on Day 28, and  $AUC_{0-24}$  increased by approximately 58-fold on Day 14 and 159-fold on Day 28. For 15 mg q.d. dosing,  $C_{max}$  increased by approximately 14-fold on Day 14 and 16-fold on Day 28, and  $AUC_{0-24}$  increased by approximately 72-fold on Day 14 and 82-fold on Day 28.

The exposure ratio ( $AUC_{0-24}$ ) between the 10 mg and 15 mg dose group is in a range of about 4.7 fold. This should provide a sufficient safety margin in renally impaired subjects receiving a dose of 10 mg q.d., taking into consideration that a 4.7 fold higher exposure was also well tolerated in healthy subjects.

Taken together no specific drug-related risks are anticipated. Still, the following safety measures will be applied in this study in order to minimize the risk for the participating subjects:

- There will be a staggered inclusion of renal impaired subjects starting with a cohort of 3 subjects. The remaining subjects with renal impairment will enter the trial at least 14 days apart after the principal investigator and sponsor have evaluated safety and PK data up to 1 week after start of treatment from this initial cohort.
- Over the entire period the subjects will be under close medical observation either during the hospitalization and ambulatory phase (see [Flow Chart](#)).
- Although rare, a potential for drug-induced liver injury (DILI) is under constant surveillance by sponsors and regulators. Therefore, this trial requires timely detection,

Proprietary confidential information © 2018 Boehringer Ingelheim International GmbH or one or more of its affiliated companies

evaluation, and follow-up of laboratory alterations in selected liver laboratory parameters to ensure subjects' safety, see also [Section 5.2.2.1](#).

Healthy subjects and subjects with moderate renal impairment are not expected to have direct medical benefit from participation in this MRD trial with BI 1467335. However, it is considered that all subjects participating in the study will not be exposed to undue risks and adverse events in relation to the information expected from this trial. Considering the medical need of the development of an effective and well tolerated drug for the therapy of NASH, the benefit of this trial is considered to outweigh the potential risks and justifies the exposure of healthy and renally impaired subjects at the intended dose levels and treatment duration.

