2 	28	647:55	07:55		x 	x		x 	x 	x 
		648:00	08:00	Last drug administration 			▲			
		648:15	08:15		x		x			
		648:30	08:30		x		x	x		
		648:45	08:45		x		x	x		
		649:00	09:00		x		x	x	x	x
		649:30	09:30		x		x			
		650:00	10:00	240 mL fluid intake and light breakfast 	x		x	x	x	x
		651:00	11:00		x					
		652:00	12:00	240 mL fluid intake, thereafter lunch 	x	+	x	x	x	x
		654:00	14:00		x					
		656:00	16:00	Snack (optional) 	x	+	x	x	x	x
		658:00	18:00	Dinner 	x					
		660:00	20:00		x	+	x	x	x	x
	29	672:00	08:00		x	▼	x	x	x	x
		673:00	09:00	Discharge from trial site (confirmation of fitness) 	x	x		x	x	x
30	696:00	08:00	Ambulatory visit		x					x
31	720:00	08:00	Ambulatory visit		x					x
33	768:00	08:00	Ambulatory visit		x					x
35	816:00	08:00	Ambulatory visit		x					x
3	38 to 41	9999:00	08:00	End of trial (EOT) examination 	x	x		x	x	x

Proprietary confidential information © 2018 Boehringer Ingelheim International GmbH or one or more of its affiliated companies

1. Screening includes subject information, informed consent, physical examination, check of vital signs, ECG, safety laboratory (including drug screening, pregnancy test and assessment of eGFR), demographics (including determination of body height and weight, smoking status and alcohol history), relevant medical history, concomitant therapy and review of inclusion/exclusion criteria.
2. The time is approximate; the respective procedure is to be performed and completed within 2 h prior to drug administration.
3. If several actions are indicated at the same time point, the intake of meals will be the last action. ECG recording must be conducted before any blood sampling is performed.
4. End of trial examination includes physical examination, body weight, vital signs, ECG, safety laboratory, recording of AEs and concomitant therapies.
5. Urine drug screening and alcohol breath test as well as pregnancy test in all women of childbearing potential will be done at this time point.
6. AEs and concomitant therapies will be recorded throughout the trial, but will be specifically asked for at the time points indicated in the [Flow Chart](#) above.

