### **3. DESCRIPTION OF DESIGN AND TRIAL POPULATION**

#### **3.1 OVERALL TRIAL DESIGN AND PLAN**

The study will be performed open-label, in a multiple-dose, matched group design with moderate renal impaired and healthy male and female subjects. In this exploratory study it is considered reasonable to aim for at least 25% of either gender.

It is planned to include altogether 20 participants in the trial, of which up to 10 subjects with moderate renal impairment. All subjects will receive over 4 weeks 10 mg of BI 1467335 once daily, the maximum therapeutic target dose in the upcoming phase II studies in a NASH population. Each renally impaired subject will have a healthy subject matched for gender, race, smoking status, age (within  $\pm 10\%$ ) and BMI (within  $\pm 10\%$ ). They will build a pair for later evaluation.

Renal impaired subjects will receive a subject number starting with      while healthy subjects will receive a subject number starting with

The study will follow a staggered inclusion starting with a subcohort of 3 renally impaired subjects. For this initial subcohort there will be a safety review meeting between sponsor and investigator to decide whether the study can proceed as planned. Matched healthy subjects will be only included if the corresponding renally impaired subjects have completed the study.

Additional safety reviews may be conducted at any time if deemed necessary by the investigator or sponsor.

An overview of all relevant trial activities is provided in the [Flow Chart](#). For visit schedule and details of trial procedures at selected visits, refer to [Sections 6.1](#) and [6.2](#), respectively.

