##### **3.1.1 Administrative structure of the trial**

The trial is sponsored by Boehringer Ingelheim (BI) Pharma GmbH & Co. KG, Germany.

BI has appointed a Trial Clinical Monitor, responsible for coordinating all required activities, in order to

- manage the trial in accordance with applicable regulations and internal SOPs,
- direct the clinical trial team in the preparation, conduct, and reporting of the trial,
- ensure appropriate training and information of local clinical monitors (CML), Clinical Research Associates (CRAs), and participating trial sites.

The trial medication will be provided by the Clinical Trial Supplies Unit (CTSU), BI Pharma GmbH & Co. KG, Biberach, Germany.

The trial will be conducted at  
under the supervision of the Principal Investigator.

Safety laboratory tests will be performed by the local laboratory of the trial site

The analyses of BI 1467335 (and its metabolites and stability) concentrations in plasma will be performed at the Department of Drug Metabolism and Pharmacokinetics, BI Pharma GmbH & Co. KG, Biberach, Germany.

On-site monitoring will be performed by BI or a contract research organisation appointed by BI.

Data management and statistical evaluation will be done by BI according to BI SOPs.

Tasks and functions assigned in order to organise, manage, and evaluate the trial are defined according to BI SOPs. A list of responsible persons and relevant local information can be found in the ISF.

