### **5.2.3 Assessment of safety laboratory parameters**

For the assessment of laboratory parameters, blood and urine samples will be collected by the trial site at the time points indicated in the [Flow Chart](#) after the subjects have fasted for at least 10 h. Overnight fasting is not required at the discretion of the investigator or designee for retests.

The parameters that will be determined are listed in [Tables 5.2.3: 1](#) and [5.2.3: 2](#). Reference ranges will be provided in the ISF, Section 10.

Manual differential white blood cell count or urine sediment examinations will only be performed if there is an abnormality in the automatic blood cell count or in the urinalysis, respectively.

Proprietary confidential information © 2018 Boehringer Ingelheim International GmbH or one or more of its affiliated companies

Table 5.2.3: 1

Routine laboratory tests

Functional lab group	Test name
Haematology	Haematocrit Haemoglobin Red blood cell count (RBC) Reticulocyte count White blood cell count (WBC) Platelet count Neutrophils, eosinophils, basophils, monocytes, lymphocytes
Automatic WBC differential (relative and absolute)	
Manual differential WBC (if automatic differential WBC is abnormal and considered by the investigator clinically relevant )	Polymorphnuclear neutrophils (segs), band neutrophils (stabs), eosinophils, basophils, monocytes, lymphocytes
Coagulation	Activated partial thromboplastin time (aPTT) Prothrombin time (Quick's test and INR) Fibrinogen
Enzymes	Aspartate transaminase (AST/GOT) Alanine transaminase (ALT/GPT) Alkaline phosphatase (AP) Gamma-glutamyl transferase (GGT) Glutamate dehydrogenase (GLDH) Creatine kinase (CK) CK-MB, only if CK is elevated Lactate dehydrogenase (LDH) Lipase Amylase
Hormones 	Thyroid stimulating hormone (TSH) ft3, ft4
Substrates 	Plasma glucose Creatinine (+ calculation of eGFR by CKD-EPI) Cystatin Total bilirubin Direct bilirubin Total protein Protein electrophoresis (only at screening examination)
	Albumin Alpha-1-Globulin Alpha-2-Globulin Beta-Globulin Gamma-Globulin C-Reactive Protein (CRP) Uric acid Total cholesterol Triglycerides
Electrolytes	Sodium Potassium Chloride Calcium Inorganic phosphate

Proprietary confidential information © 2018 Boehringer Ingelheim International GmbH or one or more of its affiliated companies

**Table 5.2.3: 1** Routine laboratory tests (cont).

Functional lab group	Test name

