- $\lambda_{z,N}$  (terminal rate constant in plasma following N doses)
- $t_{1/2,N}$  (terminal half-life of the analyte in plasma following N doses)
- $MRT_{ex,N}$  (mean residence time of the analyte in the body following N orally administered doses)
- $CL_{N}/F$  (apparent clearance of the analyte in the plasma following N doses of extravascular administration; calculated as Dose/ $AUC_{0-24,N}$ ), *for BI 1467335 only*
- $V_{z,N}/F$  (apparent volume of distribution during the terminal phase  $\lambda_z$  following N doses of extravascular administration; calculated as  $CL_{N}/F/\lambda_{z,N}$ ), *for BI 1467335 only*
- $R_{A,Cmax,N}$  (accumulation ratio based on  $C_{max}$  after N doses)
- $R_{A,AUC,N}$  (accumulation ratio based on  $AUC_{\tau}$  after N doses)
- $Ae_{t1-t2,N}$  (amount of analyte that is eliminated in urine following N doses from the time point  $t_1$  to time point  $t_2$ )
- $fe_{t1-t2,N}$  (fraction of analyte eliminated in urine following N doses from time point  $t_1$  to time point  $t_2$ )
- $CL_{R,t1-t2,N}$  (renal clearance of the analyte in plasma from the time point  $t_1$  to time point  $t_2$  following N doses)

On days 2, 4, 7, 10, 14, 15, 17, 21, 25, 26 and 28:

- $C_{pre,N}$  (predose concentration of the analyte in plasma immediately within 30 minutes before administration of the  $N^{th}$  dose)

Further pharmacokinetic parameters might be calculated as appropriate.

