### **7.3.4      Interim analyses**

No interim analysis is planned. However, as mentioned in [Section 2.3](#) a staggered inclusion of renally impaired subjects will be applied, where based on the safety and PK data of the first 3 subjects up to one week after start of dosing, it will be decided whether the remaining subjects can be dosed. For this purpose exploratory evaluation of safety and PK data will be performed.

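### The review that releases the remaining renally impaired subjects closes at one week, six days before the first scheduled on-treatment safety laboratory sample, and nothing requires that result to be seen first

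*Protocol*

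**What the plan says.** Protocol Section 2.3 (drug-related risks and safety measures) plans an initial cohort of 3 renally impaired subjects. The others enter at least "14 days apart after the principal investigator and sponsor have evaluated safety and PK data up to 1 week after start of treatment". Section 7.3.4 gives the same cut-off for the decision on dosing the rest: "based on the safety and PK data of the first 3 subjects up to one week after start of dosing, it will be decided". Section 3.1 adds "For this initial subcohort there will be a safety review meeting between sponsor and investigator to decide whether the study can proceed as planned", with no cut-off or interval.

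The same list in Section 2.3 asks for timely detection, "evaluation, and follow-up of laboratory alterations in selected liver laboratory parameters". The hepatic AESI (5.2.2.1) and removal rule 4 (3.3.4.1) are both defined through liver laboratory values. Renal function is part of the safety panel: Table 5.2.3: 1 lists "Creatinine (+ calculation of eGFR by CKD-EPI").

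Section 5.2.3 leaves the timing of safety laboratory samples to the Flow Chart. The chart has them at screening, Day -2 and Day 1 pre-dose, and then at Day 14 pre-dose (311:55).

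**The concern.** The review is the planned decision point before most of the impaired group is dosed. A reader would expect it to include at least one laboratory result obtained on treatment, given that the same section calls for liver laboratory surveillance and the population has reduced renal function. With a one-week cut-off and a first on-treatment sample on Day 14, it includes none. Before the review, the laboratory-defined AESI and removal rule could be met only through an unscheduled test. A change that causes symptoms would probably prompt such a test; a change without symptoms would not. What is at stake is the content of a safety decision, not the PK comparison.

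**Working it through.** **1. Which chart marks are safety laboratory and which are PK.** The columns are damaged in the extracted text, so the reading needs support.

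- The pre-dose rows of Days 1, 14 and 28 carry two marks ahead of the urine and ECG columns. The first has footnote 2 ("the respective procedure is to be performed and completed within 2 h prior to drug administration"); the second is the PK sample.
- The pre-dose rows of Days 2, 4, 7 and 10 carry a single mark there, without footnote 2.
- Section 5.5.1.3 requires a pre-dose plasma concentration "On days 2, 4, 7, 10, 14, 15, 17, 21, 25, 26 and 28". If the single Day 7 mark were a laboratory mark, the chart would have no PK sample on a day when one is required. It must be PK.
- Two weaker checks do not settle it. The single mark sits where the Day 1 profile times (0:15 to 12:00) have theirs, but the undisputed laboratory marks at screening and Day -2 are in that position too. On blood volume, 69 PK samples × 2.7 mL = 186.3 mL; with 3 mL for pharmacogenomics, 300 − 186.3 − 3 = 110.7 mL is left. That suits a few laboratory visits rather than one at every mark, but does not by itself exclude a Day 7 sample.

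**2. The plan's own times.** Pre-dose time = (day − 1) × 24 h − 5 min. Day 7: 6 × 24 h − 5 min = 143:55. Day 14: 13 × 24 h − 5 min = 311:55. Both match the Flow Chart.

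**3. The gap.** Cut-off: 7 × 24 h = 168:00. Then 311:55 − 168:00 = 143 h 55 min = 6.0 days. Seven doses have been taken by the cut-off (Days 1 to 7) and 13 by the Day 14 pre-dose sample. Scheduled on-treatment safety laboratory samples available to the review: 0 in each of the 3 subjects.

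**4. What the 14-day interval does.** The release covers up to 10 − 3 = 7 subjects. How many could start before the Day 14 samples depends on where the interval begins, which is not stated.

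| Interval counted from | Earliest further entry | Further subjects dosed before the Day 14 samples |
|---|---|---|
| Last first dose in the initial cohort | Day 15 (336:00 h) | 0; the sample is 336:00 − 311:55 = 24 h 5 min earlier |
| The review (Day 8 at the earliest) | Day 8 + 14 = Day 22 | 0 |
| Between later subjects only | Fourth subject Day 8, fifth Day 8 + 14 = Day 22 | About 1 |

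Under none of the three readings does the text require the Day 14 results to be reviewed before entry.

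**The case against.** The strongest reply is that the interval already does the work. On two of the three readings, no further subject is dosed before the Day 14 samples are drawn. On the third, entry on Day 8 would be hard to achieve, because the review needs PK data and plasma goes frozen to the sponsor's laboratory. The trial has one site and is open-label. "Safety laboratory tests will be performed by the local laboratory of the trial site" (3.1.1), and results arrive electronically (5.2.3). Hepatic AESIs reach the sponsor within 24 hours, and the investigator and sponsor who would see a Day 14 signal are the people who release subjects. Unscheduled tests on symptoms (5.2.2.1), extra reviews (3.1) and stopping criteria (3.3.4.2) are also available. There is no dose escalation, and Section 2.3 reports no clinically relevant laboratory changes in healthy subjects at 10 mg (9 on active) or 15 mg (5 on active).

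Most of this stands, and it is why the priority is low. A reader might infer from the release of up to 7 subjects that 7 would be dosed before any on-treatment laboratory result exists. The documents do not support that: the interval reduces the number to none or about one. Nor do they give a frequency of laboratory changes in impaired subjects, so the chance of a missed signal cannot be put into figures.

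What the reply does not supply is a rule. A sample drawn before the next entry is not the same as a result reviewed before it, and both sections that define the decision stop at one week.

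**Conclusion.** The point holds as a gap in the release rule. The decision on the remaining impaired subjects is set on data to one week, and the first scheduled on-treatment safety laboratory sample comes 6.0 days later. The 14-day interval limits actual exposure to none or about one subject, but its start is undefined and it brings no laboratory result into the decision.

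The clinical weight is modest. The primary PK estimates are unaffected, and it would be wrong to read this as an absence of early safety monitoring: AEs, vital signs, ECG and PK all fall within the first week.

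The conclusion rests on reading the single Day 7 mark as PK. The footnote pattern and Section 5.5.1.3 support this, but it should be confirmed on the original PDF. The day counts assume that the initial cohort is dosed together, or are taken from its last first dose.

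**What to change.** State the rule once in Section 2.3 and refer to it from Sections 3.1 and 7.3.4. Suggested text:

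> No further renally impaired subject receives a first dose until at least 14 days after the first dose of the third subject of the initial cohort, and until the Day 14 safety laboratory results of all 3 subjects have been reviewed together with their one-week safety and PK data.

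If the sponsor means 14 days from the review, keep that start point and add only the condition on the Day 14 results.

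**Cost.** No new visit and no new sample. The delay occurs once. It is 0 days if the interval already runs from the cohort's last first dose, assuming the laboratory reports within about 24 h, and 0 days if it runs from the review. If it was meant only between later subjects, the delay is up to Day 15 − Day 8 = 7 days.

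**Weaker alternative.** Keep the one-week cut-off and add a safety laboratory sample at the existing Day 7 pre-dose visit in the first 3 subjects. Its volume must fit the roughly 300 mL total in Section 2.3. It would precede much of the accumulation: at 10 mg, Section 1.2 reports AUC over 24 h about 58-fold higher by Day 14 and 159-fold by Day 28 than on Day 1.
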